1.0 Objectives*

- 1.1 This is a single-arm observational trial of a new FDA-approved device (Compass Vascular Access device, Centurion Medical Products, Williamston MI; formerly Mirador Biomedical). This device is a compact, sterile, single-use extravascular blood pressure transducer with a continuous digital pressure display. This pressure measurement provides an aid in the confirmation of appropriate venous access. The device has FDA 510(k) clearance as substantially equivalent to existing devices on the market. Evidence of this clearance is included with this application.
- 1.2 The investigators plan to enroll 40 consenting patients with $\text{BMI} \geq 35$ who require central venous catheterization for clinical reasons independent of the existence of this study. For purposes of the study, the investigators will record data germane to the procedure as well as operator satisfaction. Analysis of these data will be used to evaluate the appropriateness of the device for this procedure in the obese population, where device ergonomics may be more of a factor than in previous studies.
- 1.3 This study is not investigating the safety of the device, because the primary outcome is operator satisfaction. None of the observed outcomes relate directly to device safety, and the study is not powered to detect rare adverse events.
- 1.4 This study is also not investigating the effectiveness of the device. The investigators are not gathering any data that would permit evaluation of the device's accuracy or precision, which are the salient factors for effectiveness of a measurement device.
- 1.5 Deidentified study data may be shared with the sponsor, but the investigators do not plan to submit study data to the FDA.

2.0 Background*

Central venous catheterization (CVC) is a common perioperative procedure that is associated with a number of potential mechanical complications. It involves three steps: first a needle is introduced to the target vein, followed by a guidewire, and finally the catheter itself. The needle is relatively fine, and the guidewire slightly larger, but the catheter is relatively large, with corresponding increases in the severity of complications associated with arterial puncture. Inadvertent arterial cannulation is the most common mechanical complication of CVC placement and is associated with significant morbidity and mortality.(1) Complications of arterial puncture or cannulation may lead to uncontrolled hemorrhage, airway compromise related to neck hematoma, cerebrovascular accident, hemothorax, mediastinal bleeding, cardiac tamponade, aortic dissection, and death.

The use of ultrasound guidance for CVC has mitigated the risk for arterial cannulation but not eliminated it. Ultrasound guidance has decreased the rate of arterial puncture to rates as low as 0.5%.(1) Nonetheless, arterial cannulation can still occur during CVC placement with ultrasound guidance for a variety of reasons primarily

Compass Device Trial

related to either incorrect identification of the target vein or the inability to accurately determine the location of the tip of the access needle.(2)

Due to the limitations of two-dimensional surface ultrasound and the goal of further mitigating the risk of arterial access during CVC insertion, various methods have been employed to confirm that only the target vein has been accessed. One method is echocardiographic confirmation of guidewire placement in the superior vena cava and/or the right heart; however, aside from select operative procedures, use of echocardiography in the perioperative period or in the intensive care unit (ICU) is limited, costly, and may not be contemporaneous with CVC placement. A second method is the use of column manometry to transduce the intravascular pressure. However, performance of manometry may be cumbersome and may generate a false negative finding (fluid column appears venous) even when the CVC is intra-arterial due to obstruction of the proximal transduction site or a low cardiac output state.

An FDA-approved electronic extravascular blood pressure monitor (Compass® Vascular Access device, Centurion Medical Products, Williamston, Mi.) has been recently developed which provides an aid in the confirmation of appropriate CVC access. The device is a compact, sterile, single-use pressure transducer that has a continuous digital pressure (mmHg) display. The device connects in a luer-lock fashion to all standard syringes and needles and has a separate self-sealing channel for CVC guidewire insertion and withdrawal. The device is intercalated between the syringe proper and the needle used to access the target vessel. The device permits confirmation of guidewire insertion into the target vein via its pressure display. There are two previous reports on the use of this device in the perioperative and ICU settings.(3,4) In the report by Togashi et al(3), 298 CVC placements were performed with the device and five inadvertent arterial punctures occurred even though ultrasound guidance was utilized. All five of these inadvertent arterial punctures were correctly identified prior to cannulation because of the use of the device.(3) The device did not produce any adverse events. Furthermore, Togashi et al performed a cost-benefit analysis comparing the claim costs associated with a single mechanical CVC injury (per American Society of Anesthesiology Closed Claims Database(5): \$95,000 / event) versus device costs and found that the use of the novel device generated a net savings of \$116 for each CVC insertion.(3) The Togashi group (3) noted that some operators would prefer a smaller device, but most were satisfied with it as tested. The planned case series is intended to evaluate use of the device in the obese population (BMI ≥ 35 kg/m²), where device ergonomics may be more of a factor.

References:

3.0 Inclusion and Exclusion Criteria*

- 3.1 The study population consists of obese ($\geq 35 \text{ kg/m}^2$) adult ($\geq 18 \text{ yrs}$) patients presenting at the UNM Hospital main/adult operating rooms who require central venous catheter (CVC) placement for their perioperative care. The investigators will exclude pregnant women, adults unable to consent, and prisoners.
- 3.2 Members of the commonly recognized vulnerable populations will not be enrolled: pregnant women, prisoners, neonates of uncertain viability or that are nonviable, and minors.

4.0 Study-Wide Number of Subjects*

- 4.1 The planned completed sample size is 40 patients. The investigators request HRRC permission to enroll **up to 45 patients** in order to accommodate any whose CVC procedures may be cancelled between consenting and commencement of the actual procedure, but will only complete data collection for 40 patients.

5.0 Study-Wide Recruitment Methods*

This is a single-site study; local recruitment methods are described in section 22 below.

6.0 Multi-Site Research*

- 6.1 This is a single-site study.

7.0 Study Timelines*

- 7.1 Describe:
 - A given individual will participate in the study for approximately 15 minutes, representing the time required for the CVC placement.
 - The investigators anticipate that the study sample can be enrolled in approximately six months to one year.
 - The investigators estimate that all analyses will be completed in one year after completion of enrollment.

8.0 Study Endpoints*

- 8.1 This is an observational study. The main data point of interest is operator satisfaction. The number of inadvertent arterial punctures

identified by the device (if any) will also be recorded. The data collection form is included with this HRRC application.

8.2 The investigators have not identified any safety endpoints.

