9.0 Procedures Involved*

9.1 This is an observational study to be completed on 40 patients meeting the inclusion/exclusion criteria. Subjects presenting for CVC placement at the UNMH operating suites will be prepared as usual and consent obtained. The Compass pressure measurement device will be included in the CVC placement apparatus as per the manufacturer's directions. Data will be recorded on the placement procedure as well as routine patient demographic data. Identifiers will not be recorded.

9.2 A photograph of the device (with attached syringe and needle) is below.

9.3 The only research procedure is the inclusion of the device in the CVC placement apparatus, for patients who would already be having CVC placement regardless of the existence of this study. The research does not modify routine practice surrounding CVC placement (patient selection and preparation, operating personnel, catheter equipment, the procedure itself, or medications used) in any way. These considerations should mitigate risks.

9.4

- As noted above, enrollment of subjects from a population already presenting for CVC placement regardless of the existence of this study mitigates study risks. The investigators are similarly not modifying routine CVC practice except to specify the use of the studied device.
- The project does not specify the use of any drugs. The device being studied is the Compass for CVC pressure transducer device (Centurion Medical Products, Williamston MI).
- The data collection form is included with this application.

9.5 Data to be collected include routine demographic data (age, sex, height, weight, BMI, ASA status), data surrounding the CVC placement procedure (insertion location, use of ultrasound guidance, venous pressure before/after guidewire placement, operator satisfaction), and incidence of inadvertent arterial puncture.

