10.0 Data and Specimen Banking*

- 10.1 Data will be recorded on paper forms with identifiers in order to permit resolution of any incomplete/unclear data entries. Data will be deidentified upon transfer to an electronic spreadsheet for analysis. The identifiable data forms will be retained until publication of results in order to permit any supplemental analyses requested by peer reviewers. The deidentified data may be retained indefinitely for potential future use, such as in serving as the underlying dataset for power analysis of a future study.
- 10.2 Deidentified data may be reviewed by the study sponsor. Release of deidentified data may be requested by contacting the PI and/or sponsor. Both the PI and study sponsor must approve release. Release will only be made to personnel who are qualified researchers pursuing legitimate research projects, in the opinion of the PI and/or sponsor. Identifiable data will not be released except as required by law.

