11.0 Data Management* and Confidentiality

- 11.1 Data will be summarized by reporting mean (SD) of continuous variables such as BMI and age, percentages for categorical data such as patient sex, and raw count for inadvertent arterial punctures.
- 11.2 As this is an observational study, a power analysis is not useful.
- 11.3 All investigators are CITI- and HIPAA-certified. Completed data collection forms will be maintained in locked cabinets in Anesthesiology department offices, which are a patient-restricted area. As noted in section 10 above, the deidentified data will be retained indefinitely. Only investigators will have access to study data, but they will transmit an electronic copy of deidentified study data to the sponsor upon request. Qualified researchers may request an electronic copy of the deidentified data as listed in section 10 above. Identifiable data will not be released except as required by law.

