14.0 Risks to Subjects*

- 14.1 Previous studies on this sterile, single-use device have identified no adverse events arising due to its use. The only issue identified to date is the size of the device; a few operators (reported in reference 3 listed above) would prefer that it be smaller. It is therefore possible, but has not ever been demonstrated, that the device's presence may impede CVC placement in some way. This risk is completely reversible, because the device can simply be removed from the needle apparatus if it is in the way. As in any study, there are risks of confidentiality breach. This study does not gather data that are especially sensitive, so the consequences of any confidentiality breach are minor. All risks are mitigated to the extent possible by restricting enrollment to a population that would have received CVC placement regardless of the existence of this study.
- 14.2 The presence of the device in the needle apparatus may present some unforeseeable risk, but as noted above, no such risks have been reported, and the device can simply be removed so that the CVC placement can proceed as usual.
- 14.3 The investigators have not identified any risks to the embryo or fetus should a subject be pregnant at the time of the study.
- 14.4 The investigators have not identified any risks to others who are not subjects.

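### Does it matter that section 8.1 limits the arterial puncture count to punctures the device identified, while 9.5 and 11.1 do not?

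*Protocol*

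**What the plan says.** The protocol names the item in three places.

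- Section 8.1, after calling operator satisfaction the main data point, says that the number of inadvertent arterial punctures "identified by the device (if any) will also be recorded". The next sentence refers to a data collection form filed with the application.
- Section 9.5, the list of data to be collected, ends with "and incidence of inadvertent arterial puncture".
- Section 11.1, on how data will be summarised, ends with "and raw count for inadvertent arterial punctures".

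Other sections bear on the weight of the item. Section 1.3 makes operator satisfaction the primary outcome and says the study does not investigate safety. Section 1.4 says it does not investigate effectiveness and gathers no data on the device's accuracy or precision. Section 8.2 names no safety endpoint, and section 11.2 plans no power analysis. The planned completed sample is 40 patients (section 4.1).

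**The concern.** Only section 8.1 confines the count to punctures that the device identified. A puncture recognised by other means, or after the device was taken off, would enter the count under 9.5 and 11.1 but not under 8.1. A reported zero would then mean either that the device flagged none or that none was recorded at all.

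The protocol leaves room for such a case. Section 14.1 says "the device can simply be removed from the needle apparatus if it is in the way", and section 1.2 describes the obese population as one "where device ergonomics may be more of a factor than in previous studies". Neither passage says that removal is expected. Section 9.5 lists no item for how a puncture was recognised. If the form has none either, the two counts could not be separated afterwards.

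Section 10.1 also keeps the deidentified data for possible later use, "such as in serving as the underlying dataset for power analysis of a future study". A later user would want to know which event was counted.

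**Working it through.** **Reproducing the stated rate.** Section 2.0 reports five punctures in 298 placements in the earlier device study: 5/298 = 0.01678, or 1.7%, which agrees with section 15.1. Section 2.0 also gives a lower rate: "Ultrasound guidance has decreased the rate of arterial puncture to rates as low as 0.5" percent.

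**How many punctures to expect.** With n = 40 and at most one puncture per patient, the mean is n × p and P(at least one) = 1 − (1 − p)^40.

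- p = 0.005: mean 40 × 0.005 = 0.20; P = 1 − 0.995^40 = 0.18.
- p = 5/298: mean 40 × 0.01678 = 0.67; P = 1 − 0.98322^40 = 0.49.

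**When the two readings differ.** Let s be the share of punctures that the device identifies, and r the chance that a puncture it does not identify is recognised in another way. A puncture that nobody recognises enters neither count, so

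P(counts differ) = 1 − (1 − p(1 − s)r)^40.

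The protocol gives no value for r. Setting r = 1 gives an upper bound for each choice of p and s.

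**Values of s.** On the earlier study, section 2.0 says: "All five of these inadvertent arterial punctures were correctly identified prior to cannulation because of the use of the device". That is 5 of 5, so s = 1. Five events are thin evidence: the exact two-sided 95% lower limit is 0.025^(1/5) = 0.478. The value 0.9 is an assumption that is not in the protocol, used only to show the range.

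| s | p = 0.005, r = 1 | p = 5/298, r = 1 |
|---|---|---|
| 1 (5 of 5 observed) | 0 | 0 |
| 0.9 (assumed) | 0.020 | 0.065 |
| 0.478 (lower limit) | 0.099 | 0.297 |

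Even at s = 0.478 with the higher rate and r = 1, the expected gap between the two counts is 40 × 0.01678 × 0.522 = 0.35 punctures.

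**Side by side.** Section 8.1 is the endpoint statement and carries the fuller wording. Section 9.5 is an inventory of fields, and 11.1 is a single sentence on summary formats. Reading the shorter phrases as referring back to 8.1 is natural. So is recording every puncture and noting which ones the device identified. Either course can be followed without breaching any of the three passages as a collection instruction.

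**The case for a change.** The best case for a change is that the protocol itself describes the item three times, once with a limit and twice without. This is therefore not simply detail left for a later document. With up to a 49% chance of at least one puncture, the item may well be non-zero, and 5 of 5 cannot prove that the device finds every puncture. The repair would be cheap: one clause in 8.1, cross-references in 9.5 and 11.1, and at most one tick-box on the form.

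The wording difference stands, as do the low cost and the thinness of the 5-of-5 evidence. The step to a needed change does not.

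- The form governs what the operator writes down. It is not shown here, so a fault in what is recorded cannot be established.
- The text does not show which wording is the intended one. Two opposite corrections are possible: widen 8.1, or narrow 9.5 and 11.1.
- Widening 8.1 and noting for each puncture whether the device identified it would produce a detection proportion. That sits awkwardly with section 1.4, which disclaims data for judging the device's accuracy.
- Section 10.1 offers a future power analysis only as an example and does not mention punctures. With 0.20 to 0.67 expected events, 40 patients could hardly inform a puncture-rate calculation under either reading.

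**Conclusion.** No change to the plan follows. This is a clerical looseness in a descriptive item. The main outcome, the sample size and the conclusions are the same under either reading, because no rate, interval, test or decision is planned for the puncture count.

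On the one experience that the protocol documents, the two counts coincide. At an assumed 90% identified they would differ in at most 2% to 6.5% of such trials, and at the lower limit of 48% in at most 10% to 30%. These are ceilings, not expectations. They rest on at most one puncture per patient, the two rates quoted in the protocol, and the extreme assumption that every puncture the device misses is recognised in some other way.

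An analyst who follows the form and says in the report which punctures were counted removes the remaining ambiguity without an amendment.

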9.0 Procedures Involved*

9.1 This is an observational study to be completed on 40 patients meeting the inclusion/exclusion criteria. Subjects presenting for CVC placement at the UNMH operating suites will be prepared as usual and consent obtained. The Compass pressure measurement device will be included in the CVC placement apparatus as per the manufacturer's directions. Data will be recorded on the placement procedure as well as routine patient demographic data. Identifiers will not be recorded.

9.2 A photograph of the device (with attached syringe and needle) is below.

9.3 The only research procedure is the inclusion of the device in the CVC placement apparatus, for patients who would already be having CVC placement regardless of the existence of this study. The research does not modify routine practice surrounding CVC placement (patient selection and preparation, operating personnel, catheter equipment, the procedure itself, or medications used) in any way. These considerations should mitigate risks.

9.4

- As noted above, enrollment of subjects from a population already presenting for CVC placement regardless of the existence of this study mitigates study risks. The investigators are similarly not modifying routine CVC practice except to specify the use of the studied device.
- The project does not specify the use of any drugs. The device being studied is the Compass for CVC pressure transducer device (Centurion Medical Products, Williamston MI).
- The data collection form is included with this application.

9.5 Data to be collected include routine demographic data (age, sex, height, weight, BMI, ASA status), data surrounding the CVC placement procedure (insertion location, use of ultrasound guidance, venous pressure before/after guidewire placement, operator satisfaction), and incidence of inadvertent arterial puncture.

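### Does the statement in section 9.1 that no identifiers are taken, against the identifiable paper forms of section 10.1, put the data or the privacy safeguards at risk?

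*Protocol*

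**What the plan says.** Section 9.1 describes what happens at the procedure: consent, inclusion of the device, and recording of procedural and demographic data. It then adds "Identifiers will not be recorded", with no limit to a particular form, file or stage.

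Section 10.1 describes data handling in more detail:

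- On capture and its purpose, it states: "Data will be recorded on paper forms with identifiers in order to permit resolution of any incomplete/unclear data entries".
- Removal of identifiers comes at a later step, when the paper data are entered into the spreadsheet used for analysis.
- On how long the paper is kept, it states: "The identifiable data forms will be retained until publication of results". The reason given is that peer reviewers may ask for further analyses.

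Section 10.2 allows deidentified data to be shared under conditions and bars release of identifiable data outside legal requirements. Section 11.3 keeps the completed forms locked in a restricted area and repeats that "Identifiable data will not be released except as required by law". Section 14.1 lists a confidentiality breach among the risks. Section 9.5 lists the items to be collected; none is a name or record number.

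**The concern.** Sections 9.1 and 10.1 both speak of recording the same data and give opposite instructions, so staff cannot obey both as written.

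If staff followed 9.1, the one route the protocol gives for settling an incomplete or unclear entry would be gone. In a series of 40 completed patients there is little data to spare. Operator satisfaction, the main data point, is collected around a procedure of about 15 minutes, and a form with no identifier may not show later which case or operator to ask.

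If staff followed 10.1, identifiable forms for up to 45 patients would be kept for the whole enrolment period (six months to a year), through an analysis period put at a year, and until publication. Meanwhile 9.1 would be telling the review board that no such records are made. At stake would be either data that cannot be recovered or a privacy statement that is not true.

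**Working it through.** The plan gives no figure to reproduce here, and no sample-size calculation depends on the point (section 11.2: "As this is an observational study, a power analysis is not useful"). The check is a comparison of text, followed by a bound on the loss.

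**1. Which sentence governs?**

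| Section | Identifiable records exist? | Detail given |
|---|---|---|
| 9.1 | No | One sentence, no reason, no procedure |
| 10.1 | Yes, on paper | Purpose, point of removal, retention period |
| 10.2 | Assumed yes | Rule on release |
| 11.3 | Assumed yes | Storage, access, rule on release |

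Three sections form one consistent arrangement: identifiable locked paper, then a deidentified spreadsheet. Only 9.1 departs from it. Its sentence would be true of the electronic analysis file, although its wording is about recording and does not say so.

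**2. What would be lost if 9.1 were followed literally?**

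- *Supplemental analyses.* Any analysis of the 9.5 variables runs on the deidentified data, which 10.1 allows to be kept indefinitely. Only a request that needed a return to the chart would fail.
- *BMI.* Height and weight are on the same form, and BMI = weight (kg) / height (m)². A missing or illegible BMI can be rebuilt without the chart.
- *Operator satisfaction.* This is an opinion. The documents give no reason to expect it in the chart, so a chart look-up is not shown to protect it. A query at the bedside needs no stored identifier.
- *Other items*, such as insertion site or arterial puncture. A late query could indeed fail.

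**3. How large is the loss from one failed query?**

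Input: 40 completed patients (section 4.1). Losing a whole patient would cost 1/40 = 2.5% of the sample. But section 11.1 summarises each variable separately (mean and SD, percentage, or count), so one unclear item removes one value from one variable: 39 of 40 remain there, and 40 of 40 for every other variable. For that one variable, with the spread unchanged, the standard error rises by a factor of √(40/39) = 1.013, or about 1.3%. The documents give no rate of unclear entries, so an expected total loss cannot be stated.

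**4. What does the review board see if 10.1 is followed?**

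The same protocol tells it of identifiable forms, how long they are kept, how they are stored and who may receive data (10.1, 10.2, 11.3), and of the confidentiality risk (14.1).

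**The case for a change.** The strongest case for acting is that the contradiction is plain, applies to every patient and is cheap to remove. Section 9.1 concerns what is captured at the procedure, while 10.1 removes identifiers only afterwards. The list in 9.5 names no direct identifier, which fits the literal reading of 9.1. Whether identifiable records exist matters to a confidentiality review. A study number on each form, with a separate locked link log, would allow queries to be settled without identifiers on the forms.

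Some of this stands. The sentences conflict as written, nothing in the protocol limits the one in 9.1, and a late query on an unidentified form could fail. The claim that data would be lost in any important amount does not stand: the supplemental analyses remain possible, BMI can be rebuilt, and an unclear item does not remove a patient. Nor is the review board left unaware. The link log is a reasonable preference, but it would replace an arrangement that is already coherent in 10.1 and 11.3, and no conclusion of the study would differ under it.

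**Conclusion.** This is a clerical slip and needs no change to the plan. One sentence in 9.1 disagrees with 10.1, 10.2 and 11.3, and those three sections agree with each other and give enough detail for staff to act on. No endpoint, summary or safety provision differs between the two readings. The worst effect of one unresolved query is one value of one variable out of 40. If the protocol is revised for other reasons, the sentence in 9.1 could be brought into line with 10.1, but nothing in the results depends on it.

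This rests on two assumptions. The first is that staff work from the detailed handling rules in 10.1 and from the data collection form, which is not among the documents, so its fields cannot be checked. The second is that unclear entries are few, for which the documents give no rate.
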